8.4.2.1. Elevated Liver Enzymes

An increase in AST or ALT to $>3\times$ baseline (and $>ULN$) or total bilirubin $>2\times$ baseline (and $>ULN$) should be followed by repeat testing within 48 to 72 hours to confirm the abnormalities and to determine if they are increasing or decreasing. Adverse event information should also be collected. If symptoms persist or repeat testing shows AST or ALT $>3\times$ baseline (and $>ULN$) or total bilirubin $>2\times$ baseline (and $>ULN$), subjects should be followed as clinically indicated depending on other laboratory and clinical signs and symptoms. The Investigator should obtain a history of concomitant medications (including nonprescription medications and herbal and dietary supplement preparations) and other possible causes of liver enzyme and bilirubin increases. Any potentially hepatotoxic medications should be identified and discontinued if advisable.

The Medical Monitor should be contacted, as appropriate.

8.4.3. Withdrawal of Consent

If the subject decides that it is in his/her best interest to discontinue from the study, he or she may withdraw consent. It is fully understood that all subjects volunteer for the study and that they may withdraw their consent to continue in the study at any time.

A reasonable effort must be made to determine the reason(s) for subject discontinuation. This information and date must be recorded in the appropriate case report form (CRF).

8.4.4. Lost to Follow-up

If a subject fails to return to the clinic for a study visit, and the Investigator ceases to have contact with the subject, he or she will be withdrawn from the study.

A reasonable effort must be made to contact the subject and determine the reason(s) why a subject fails to return for a study visit or is lost to follow-up. This information and date of contact must be recorded in the appropriate CRF.

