8.4.2. Other Reasons for Discontinuation of Study or Investigational Product

Subjects that discontinue investigational product are expected to continue in the study until the end of the study, and the study will only terminate at the time when the needed number of adjudicated events has accrued or at the discretion of the Sponsor. If a subject reaches an event, he or she should continue the regular visit schedule and continue taking investigational product as long as the Investigator assesses it as safe. Subjects who choose to discontinue investigational product prior to termination of the study need to also continue to follow the regular visit schedule

through to study closure. In general, subjects should be strongly encouraged to both stay on investigational product and remain in the study until study termination. Early termination procedures should only be conducted if the subject withdraws consent (See [Section 9.7.18](#) Early Discontinuation and/or Early Termination Procedures).

The following events are considered appropriate reasons for a subject to discontinue investigational product; however, these subjects are expected to continue in the study until study termination and the study will only terminate at the time when the needed number of adjudicated events has accrued (or at the discretion of the Sponsor):

- Subject begins treatment with commercially available OCA
- The Investigator or Sponsor considers that it is advisable or in the best interest of the subject.
- The occurrence of clinical or laboratory AEs considered by the Investigator to be clinically important safety concerns and related to study drug.
- Withdrawal of consent
 - Consent may be fully withdrawn (in which case the subject discontinues both investigational product and study visits and procedures).
 - Consent may be modified to discontinue study visits but allow semi-annual telephone contact.
 - Consent may be modified to discontinue study visits or semi-annual telephone contact but allow continued access to medical records to assess for potential adjudicated hepatic and/or cardiovascular events.

Subjects who undergo a liver transplant during the course of the study must discontinue investigational product and discontinue the study visit schedule. However, these subjects should be encouraged to consent to the semiannual telephone contact and/or continued record review only to allow for secondary outcome events data to be collected.

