9.7.2. Informed Consent Procedures

The Investigator or designee will explain the nature, purpose, possible risk and benefit of the study to the subject and will provide him/her with a copy of the written information and informed consent form (ICF). The subject will be given sufficient time to consider the study before deciding whether or not to participate. The subject will be informed that participation is

voluntary and that her/his future medical treatment will not be compromised by participation in the study and that s/he can withdraw from the study at any time. The subject must be willing and able to provide written informed consent before entering the study. The Investigator or a medically qualified designee is responsible for administering and documenting the written informed consent of the subject. The subject will be given a copy of the written information and his/her signed and dated consent form.

Any change in a subject's consent status (eg, semi-annual telephone contact or medical record review) must be documented in a signed informed consent form or addendum. The subject will be given a signed and dated copy of the consent document.

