Early Termination	Discontinued	Withdrawn	No additional visits except EOT/EOS	Combined Visit, Completed as close as possible to last dose IP	
Treatment Discontinuation^b	Discontinued	Active	Regular Visit Schedule	Complete as close as possible to last dose IP	Complete at Final study visit
	Discontinued	Semiannual contact ^c	Telephone contact every 6 months (± 2 weeks)	Combined Visit, Completed as close as possible to last dose IP	
	Discontinued	Record review only ^c	Record review only	Combined visit Completed as close as possible to last dose IP	
Sponsor Termination	Discontinued	N/A	No additional visits except EOT/EOS	Combined visit Completed as close as possible to last dose IP	
Pregnancy	Interrupted	Retained	Regular Visit Schedule	Complete as close as possible to last dose IP	Complete at Final study visit
	Discontinued	Complete per the above scenarios - Early Termination or Treatment Discontinuation			
Lost to Follow-up	Discontinued	LTF	None	Unable to complete due to LTF status	

EOS = end of study; EOT = end of treatment; IP = investigational product

^a Refer to [Section 7.1.2](#) Schedule of Study Procedures, [Table 2](#) for all procedures and evaluations required at the End of Treatment and End of Study Visits.

^b Includes initiation of commercially available OCA.

^c Outcomes data to be discussed or collected include data related to adjudicated hepatic and cardiovascular event-related data. No additional data (e.g. AE, concomitant medication, etc) data will be collected, except as indicated in [Section 12.1.7](#).

Some assessments noted below may be omitted if they have been completed within the 6 months (or the timeframe otherwise specified) and so long as safety issues do not warrant repeat testing.

Prior to the EOT/EOS Visit:

If possible to do before the visit, when scheduling the EOT/EOS visit, reiterate dosing instructions and advise the subject:

- If applicable, NOT to take investigational product on the morning of the next visit, and
- To bring the investigational product bottle(s); if applicable, s/he will dose at the clinic, and

- To fast overnight (at least 8 hours) prior to the next visit. Fasting is required prior to all study visits, but water is permitted.

During the EOT/EOS Visit:

- Perform a physical examination (including smoking and alcohol consumption habits).
- Perform assessment for calculation of Mayo Risk Score.
- Perform assessments for calculation of Child-Pugh Score.

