12.1.7. Notification of Post-Study SAEs

If an Investigator becomes aware of an SAE that may be attributable to the investigational product at any time after the end of the study, the SAE must be reported to the Sponsor immediately (ie, within 24 hours).

All SAEs that occur within 30 days following the cessation of investigational product, whether or not they are related to the investigational product, must be reported to the Sponsor within 24 hours by following the instructions provided in [Section 12.1.4.2](#).

SAEs that occur more than 30 days after a subject has discontinued study medication, and are not considered related to investigational product, must still be reported in the EDC system; however, these events are not required to be reported within 24 hours. At a minimum, the SAE term, event start and end date, severity, relationship to investigational product, action taken with study medication, treatment, outcome, and potential endpoint status need to be recorded in EDC for the SAE. Additional information (e.g. event summary, SAE details) may also be required to be entered, when requested by the sponsor.

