13.1.10. Handling of Dropouts or Missing Data

Subjects who discontinue investigational product are expected to continue in the study until study termination.

Missing data will be assumed to be missing at random. In order to determine the effect of missing data on the analysis, efficacy endpoints will be analyzed using different methods of imputation as described below.

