13.1.10.1. Time to Event Endpoints

For the time to event analyses, subjects who do not experience an event will be censored at the time of their last contact. Subjects with no data after randomization will be considered to have an event on Day 1 (first day of investigational product dosing).

For analyses of the percentage of subjects with an event, subjects with no data after randomization will be considered to have an event.

All time to event endpoints include only adjudicated events. Sensitivity analyses may consider all events regardless of adjudication. Events with discrepant adjudication will be analyzed using both results.

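### Subjects lost to follow-up are withdrawn with no planned search for death, transplant or hepatic admission, although they have not withdrawn consent

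*Protocol*

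**What the plan says.** All references are to the protocol.

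- **Section 8.4.4** sets two conditions, a missed visit and the end of contact. Once both hold: "and the Investigator ceases to have contact with the subject, he or she will be withdrawn from the study". The effort it requires is: "A reasonable effort must be made to contact the subject and determine the reason(s) why a subject fails to return". Section 8.4.5 repeats that effort. Neither section asks for vital, transplant or hospital status.
- **Section 9.7.18, Table 7**, lost-to-follow-up row: the study visit status is none and the end-of-treatment/end-of-study entry reads "Unable to complete due to LTF status". Semiannual telephone contact and record review are separate rows, tied to modified consent.
- **Section 8.4.2** lists, under withdrawal of consent, an option to stop visits and calls but "allow continued access to medical records to assess for potential adjudicated hepatic and/or cardiovascular events". Under **Section 9.7.2** any change in consent status "must be documented in a signed informed consent form or addendum".
- **Section 12.1.7** requires SAEs arising more than 30 days after study drug is stopped to be entered in EDC, and among the items needed are "outcome, and potential endpoint status need to be recorded in EDC for the SAE".
- **Section 13.1.10.1**: "subjects who do not experience an event will be censored at the time of their last contact". **Section 13.1.10**: "Missing data will be assumed to be missing at random".

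**The concern.** The primary endpoint (Section 13.1.3) combines all-cause death, liver transplant, MELD score of at least 15, hepatic hospitalisations, uncontrolled ascites and hepatocellular carcinoma, over an expected minimum follow-up of about 6 years. Several of these can be established without a visit: death, transplant and admission all leave records. They are also plausible reasons for contact to end. A subject who has died, been transplanted elsewhere or become too ill to attend looks, from the clinic, like any other subject who cannot be reached.

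If such subjects are withdrawn and censored at last contact with nobody looking further, the analysis treats their later risk as equal to that of subjects who stayed. Where loss follows deterioration, that is wrong, and the Kaplan-Meier curves are too favourable. The hazard ratio is biased if the link between loss and deterioration differs by arm. No analysis in the SAP can recover outcomes that were never collected.

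The rule also sits awkwardly with Sections 7.4.2 and 8.4.2, which expect subjects to stay in the study to its end and encourage even transplanted subjects to agree to telephone or record follow-up.

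**Working it through.** **1. What each kind of subject gets after visits stop (Sections 8.4.2 and 8.4.4, Table 7)**

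- Stops study drug, consent active: regular visits.
- Restricts consent to semiannual contact: telephone call every 6 months for outcome events.
- Restricts consent to records: record review for outcome events.
- Withdraws consent fully: no follow-up after a combined final visit.
- Cannot be reached, consent never changed: no planned outcome follow-up.

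The last subject is handled like a full withdrawal, without having withdrawn.

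**2. Reproducing the planned figures (Section 13.1.2)**

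Inputs: HR 0.60, two-sided 5%, 80% power, 1:1; placebo event-free proportion 0.5 at 8 years; 2 years accrual plus 6 years follow-up; about 350 subjects.

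- Events (Schoenfeld): 4 × (1.960 + 0.842)² / (ln 0.60)² = 4 × 7.849 / 0.2609 = 120.3, so **121**. Reproduced; power at 121 events is 0.802.
- Hazards: placebo ln 2 / 8 = 0.0866 per year; OCA 0.60 × 0.0866 = 0.0520 per year.
- Event probability averaged over 6 to 8 years of follow-up (uniform accrual, no loss): placebo 0.4541, OCA 0.3047, mean 0.3794.
- Expected events: 350 × 0.3794 = **132.8**, about 12 above 121.
- Subjects needed: 121 / 0.3794 = 319 with no loss; 359 with a fixed 6 years each; 340-351 with an assumed 2-3% annual loss. So 350 is consistent with the stated inputs under ordinary variants.

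**3. Events unseen after loss (illustration)**

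Section 13.1.2 states no loss rate, so the rates below are assumptions. Loss is taken as unrelated to prognosis and equal in both arms.

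- Event probability by year 2: placebo 1 − exp(−0.0866 × 2) = 0.1591; OCA 1 − exp(−0.0520 × 2) = 0.0988; mean 0.1289.
- Events forgone per subject whose observation ends at year 2: 0.3794 − 0.1289 = **0.250**. At year 1: 0.3794 − 0.0668 = 0.313.
- 5%, 10% and 15% of 350 (17.5, 35 and 52.5 subjects) at year 2: **4.4, 8.8 and 13.1** events unseen.
- Counting only subjects still event-free when lost, the figure per subject is 0.250 / (1 − 0.1289) = 0.29, giving about 5 to 15.

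With a constant annual loss instead:

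| Assumed annual loss | Share lost | Events unseen | Events seen | Power if closed at 8 years |
|---|---|---|---|---|
| 0% | 0% | 0 | 132.8 | 0.837 |
| 2% | 10.5% | 8.3 | 124.5 | 0.813 |
| 3% | 15.4% | 12.2 | 120.6 | 0.801 |
| 5% | 24.3% | 19.6 | 113.2 | 0.776 |

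If lost subjects are sicker than average, more events go unseen than shown. The resulting bias cannot be sized from the document, because it depends on why subjects are lost in each arm.

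**The case against.** Several stronger readings are tempting, and the protocol does not support them.

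- *That events in lost subjects are never counted.* No rule bars an event learned of later. Section 12.1.7 still takes late SAEs with potential endpoint status, Section 13.4 adjudicates from hospital records and death certificates, and Section 13.1.10.1 censors only subjects without an event. The effort to learn why a visit was missed may itself uncover a death or an admission. This stands. But these routes are passive: they depend on the site hearing, and routine AE collection ends with participation (Section 12.1.4.1).
- *That record review is closed to lost subjects because they cannot sign.* Section 9.7.2 asks for a signature when consent status changes. A lost subject has changed nothing and remains under the consent given at entry. The consent form is not shown and may already allow record access. What stands is narrower: neither Section 8.4.4 nor Table 7 tells the site to use records for these subjects. The access described in Sections 14.1 and 16.4 is for source verification.
- *That one missed visit is enough.* Contact must also cease, and a reasonable effort to reach the subject is required.
- *That the trial will fall short of 121 events.* It is event-driven, and Section 13.1.2.1 reviews the event rate, recruitment and retention quarterly and allows more subjects. Missed events mainly lengthen the trial; the power loss tabulated applies only if it closes at 8 years.
- *That loss will differ by arm through commercial OCA or poor tolerability.* Sections 7.4.2, 8.4.2 and 9.2.1 keep those subjects on regular visits, so differential loss is possible but not built in.

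Sensitivity analyses for informative censoring may be in the SAP and are not treated here as missing.

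**Conclusion.** The point holds in a limited form. Section 8.4.4 and Table 7 withdraw an unreachable subject and plan no active endpoint ascertainment afterwards, although consent has not been withdrawn and a record-review procedure already exists. Endpoint events after loss are likely to be missed, and censoring at last contact may be informative.

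The 121 events and roughly 350 subjects are not in error. The illustrative 4-13 unseen events of about 133 rest on an assumed 5-15% loss at year 2, exponential survival at the Section 13.1.2 rates, and loss unrelated to prognosis; they are not a forecast. Their main consequence would be a longer trial. The more serious matter is bias, whose direction and size cannot be determined from the document. This is a change that should be made because it is cheap and because the missing outcomes cannot be recovered at analysis.

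**What to change.** - **Section 8.4.4:** state that an unreachable subject who has not withdrawn consent is not withdrawn from the study, and keep loss of contact distinct from withdrawal of consent.
- **Table 7:** change the study visit status in the lost-to-follow-up row from none to record review.
- **Ascertainment:** require a search for vital status, transplant and hepatic admissions in site and usual-care records, and in public registers where law and the existing consent allow, at least once before database lock. Events found go to adjudication in the usual way.
- **Consent form:** confirm that it covers this, and add the permission if it does not.

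The cost is a protocol amendment, possibly a consent revision, and modest site time per lost subject. Local law may limit register use in some countries. The change extends an existing procedure and leaves the endpoint, the event target and the analysis as they are.

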8.4.5. Subject Discontinuation Notification

The Investigator must notify the Sponsor study monitor by telephone or email as soon as possible if any subject prematurely withdraws from the study. The date when the subject is withdrawn and the reason for discontinuation must be recorded in the CRF. If a subject is “lost to follow up” (fails to return for a visit), a reasonable effort should be made to contact the subject in order to determine why the subject failed to return. This information must be documented in the CRF. If a subject is withdrawn from the study early (regardless of the cause), all of the EOT/EOS evaluations should be performed at the time of withdrawal, as appropriate (See [Section 9.7.18](#), Early Discontinuation and/or Early Termination Procedures).

9. TREATMENT OF SUBJECTS

9.1. Investigational Product Treatment Regimen

The term investigational product refers to either OCA (provided as part of this clinical study) or matching placebo.

Two treatment groups will be evaluated: OCA and placebo. Investigational product will be administered orally. Each dose will be made up of 1 tablet (ie, one 5 mg OCA tablet or one 10 mg OCA tablet, or matching placebo).

Investigational product will be taken orally, up to once daily, for the duration of the study.

All subjects will be instructed to begin dosing on the day after the Day 0 visit (ie, on Day 1) and to take investigational product at approximately the same time of day. Subjects must be instructed to swallow the tablet whole; they must not chew, divide, or crush the tablet.

At each study visit where the daily dose of investigational product is administered at the site, all assessments, except for the post-dose collection of blood samples for the subset of subjects participating in the Month 9 PK assessment, must be completed before administration of investigational product.

9.2. Concomitant Medications

Concomitant medications (other than prohibited concomitant medications listed in Section 9.2.1) will be used at the discretion of the usual care provider (or Investigator if also the usual care provider). Relevant information about all concomitant medications (including prescribed, over-the-counter, or herbal preparations) taken prior to (ie, within 30 days of Screening) and during the study must be recorded in the source documents and CRF, as well as any dose or dose regimen changes that occur during the study. Concomitant medications should be stable prior to Day 0.

Drug Interactions

Subjects taking bile acid sequestrants (BAS, including cholestyramine and its derivatives, colestipol, colesevelam, or other sequestrants) or aluminum hydroxide- or smectite-containing antacids should be instructed to stagger their dosing of investigational product and UDCA, ensuring at least 4 hours between doses of the BAS and/or these antacids and the investigational product (and UDCA; ie, BAS should be administered at minimum 4 hours before or 4 hours after investigational product administration).

OCA taken concomitantly with warfarin may result in decreased INR levels, therefore, INR should be monitored and the dosage of warfarin adjusted, as needed during treatment with OCA and after cessation of OCA, to maintain the target INR range.

The effect of OCA on drug metabolizing enzymes has been evaluated in both in vitro and clinical studies. The PK profile of caffeine, a sensitive CYP1A2 substrate probe, showed weak effect of OCA on CYP1A2. Based on these results, OCA may increase the exposure of narrow therapeutic index drugs that are substrates for CYP1A2, such as theophylline and tizanidine.

Information related to additional drug-drug interaction (DDI) studies is available in the current version of the Investigator's Brochure (IB). The aforementioned sections of the IB should be referred to during the course of the study, and are accessible to investigators to help facilitate the assessment of potential drug-drug interactions with OCA that may be observed in study subjects.

PBC Specific Therapy

In general, Investigators will be encouraged to follow guidelines for care based upon local and institutional practice patterns and any relevant published practice guidelines. Throughout the course of the study, Investigators are expected to monitor subjects' PBC regimens and, if responsible for usual care, may adjust the regimen in order to achieve locally-appropriate treatment goals. These goals will be individualized, with the understanding that currently applicable PBC guidelines may vary among different geographic regions.

Ideally, subjects should generally remain on the baseline PBC therapies throughout the course of the study, unless the baseline PBC therapy is no longer considered clinically appropriate by the Investigator. In addition, subjects should be reminded to keep taking their blinded investigational product.

